13.3 Reporting and Exclusions

13.3.1 Evaluation of Toxicity

All subjects will be evaluable for toxicity from the time of their first treatment with study drug.

13.3.2 Evaluation of the Primary Efficacy Endpoint

Only those subjects who have measurable disease and have received at least one cycle of therapy, and have had their disease re-evaluated will be considered evaluable for response. Subjects who exhibit objective disease progression prior to removal from study will also be considered evaluable.

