5.4 Criteria for Taking a Participant Off Protocol Therapy

Duration of therapy will depend on individual response, evidence of disease progression and tolerance. In the absence of treatment delays due to adverse event(s), treatment may continue for 2 cycles or until one of the following criteria applies:

- Disease progression
- Intercurrent illness that prevents further administration of treatment
- Unacceptable adverse event(s)
- Participant demonstrates an inability or unwillingness to comply with the oral medication regimen and/or documentation requirements
- Participant decides to withdraw from the protocol therapy
- General or specific changes in the participant's condition render the participant unacceptable for further treatment in the judgment of the treating investigator

Participants will be removed from the protocol therapy when any of these criteria apply. The reason for removal from protocol therapy, and the date the participant was removed, must be documented in the case report form (CRF). Alternative care options will be discussed with the participant.

A QACT Treatment Ended/Off Study Form will be filled out when a participant is removed from protocol therapy. This form can be found on the QACT website or obtained from the QACT registration staff.

In the event of unusual or life-threatening complications, treating investigators must immediately notify the Overall PI, [name] M.D., Ph.D. at [contact].

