5.5 Duration of Follow Up

Participants removed from study due to criteria in section 5.4 will be followed for survival for 5 years or until death. . Participants removed from protocol therapy for unacceptable adverse event(s) will be followed monthly until resolution or stabilization of the adverse event.

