5.6 Criteria for Taking a Participant Off Study

Participants will be removed from study when any of the following criteria apply:

- Lost to follow-up
- Withdrawal of consent for data submission
- Death

The reason for taking a participant off study, and the date the participant was removed, must be documented in the case report form (CRF).

For Centralized Subject Registrations, the research team submits a completed Off Treatment/Off Study form to ODQ when a participant comes off study. This form can be found on the ODQ website or obtained from the ODQ registration staff.

For Decentralized Subject Registrations, the research team updates the relevant Off Treatment/Off Study information in OnCore.

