6. DOSING DELAYS/DOSE MODIFICATIONS

6.1 Toxicity Management/ Dosage Adjustments

Table 6-1 Criteria for dosing delays and re-initiation of treatment for toxicity definitely or possibly related to study drug. Based on the Common Terminology Criteria for Adverse Events (CTCAE) version 4.0.

Toxicity	Grade	Action
Cytokine Release Syndrome (CRS)	Grade 3	Withhold blinatumomab until resolved to \leq grade 1, then restart blinatumomab at 9 mcg/day with dexamethasone 8mg TID for three days. Dexamethasone will then be decreased by 25% per day until discontinued. Escalate to 28 mcg/day after 7 days and then to 112 mcg/d after an additional 7 days if the toxicity does not recur.
	Grade 4	Remove from study
Neurologic toxicity	Seizure	Discontinue blinatumomab permanently if more than one seizure occurs despite antiepileptics.
	Grade 3	Withhold blinatumomab until \leq grade 1, (mild), then restart blinatumomab at 9 mcg/day with dexamethasone (or equivalent) 20mg iv within 1 hour of start of retreatment. Dexamethasone will then be decreased by 25% per day until discontinued. Escalate to 28 mcg/day after 7 days and then to 112 mcg/d after an additional 7 days if the toxicity does not recur. If the toxicity occurred at 9 mcg/day, or if the toxicity takes more than 7 days to resolve, discontinue blinatumomab permanently
	Grade 4	Remove from study
Other clinically relevant adverse reactions	Grade 3	Withhold blinatumomab until \leq grade 1 (mild), then restart blinatumomab at 9 mcg/day. Escalate to 28 mcg/day after 7 days and then to 112 mcg/d after an additional 7 days if the toxicity does not recur. If the toxicity occurred at 9 mcg/day, or if the toxicity takes more than 7 days to resolve, discontinue blinatumomab permanently
	Grade 4	Remove from study

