11.2 Definitions

Evaluable for toxicity. All patients who receive at least one dose of study drug will be evaluable for toxicity.

Evaluable for objective response. Only those patients who have received at least one complete cycle of therapy, and have had their disease re-evaluated will be considered evaluable for response. Subjects removed from study for disease progression prior to a full cycle of therapy will also be considered evaluable for response. These patients will have their response classified according to the definitions stated below.

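### The primary response-rate denominator depends on completing cycle 1 and being restaged, is defined two ways, and does not match the enrolled counts in the Simon design

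*Combined protocol and SAP*

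**What the plan says.** Section 13.1 makes overall response rate the primary endpoint. Section 13.2 enrols 13 subjects, adds 15 if at least 6 respond, and calls the regimen worthy of further study at 15 or more responses of 28. It mentions neither evaluability nor replacement. Section 4.1 cancels the registration of anyone who receives no protocol therapy, so enrolled means treated in effect.

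Two sections define who is evaluable for response:

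- Section 13.3.2: "Only those subjects who have measurable disease and have received at least one cycle of therapy, and have had their disease re-evaluated". It then adds: "Subjects who exhibit objective disease progression prior to removal from study will also be considered evaluable".
- Section 11.2: those who "received at least one complete cycle of therapy, and have had their disease re-evaluated will be considered evaluable for response". It then adds: "Subjects removed from study for disease progression prior to a full cycle of therapy will also be considered evaluable for response".

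The 13.3.2 addition turns on leaving the study, and the documents use that term in several ways:

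- Section 5.4 lists progression, unacceptable adverse events and other reasons under "Participants will be removed from the protocol therapy when any of these criteria apply".
- Section 5.6, which sets the off-study criteria, says "Participants will be removed from study when any of the following criteria apply" and lists loss to follow-up, withdrawal of consent for data submission, and death.
- Section 5.5 opens with "Participants removed from study due to criteria in section 5.4 will be followed for survival for 5 years or until death", attaching the off-study term to the off-therapy list.
- Table 6-1 uses "Remove from study" as the action for grade 4 toxicity.

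On scanning, 11.1 ties the day 84 assessment to the conclusion of cycle 1, a 42-day infusion under 5.1. Section 10.3 and the visit schedule notes provide CT every 6 months for subjects without progression, with the first CT timed from the end-of-treatment restaging scan.

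**The concern.** Membership of the primary set is decided by what happens after treatment starts. Among subjects who stop in cycle 1, those with documented progression can be returned to the denominator. Those who stop for toxicity, die or withdraw without it cannot, and no section scores them as non-responders. If they respond less often than the subjects who are kept, the reported ORR is too high.

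The set is also not unique. Under 11.2 a subject returns only if progression was the reason for removal, and only before a full cycle. Under 13.3.2 read with 5.6, a subject who stops in cycle 1 for an adverse event is still on study and re-enters the denominator if progression is documented later. The 10.3 scans could show this. The primary denominator could then depend on how long subjects have been followed when the analysis is done.

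Finally, the error rates in 13.2 belong to 13 and 28 counted subjects. If the evaluable set is smaller, or is topped up to 28, they need not apply.

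**Working it through.** **1. The plan's own figures.** Inputs from 13.2: n1 = 13, continue at 6 or more; n = 28, success at 15 or more; p = 0.40 and 0.65.

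P(success) = Σ over x = 6..13 of P[Bin(13, p) = x] × P[Bin(15, p) ≥ 15 − x]; P(early stop) = P[Bin(13, p) ≤ 5].

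| p | P(success) | Stated | P(early stop) | Stated |
|---|---|---|---|---|
| 0.40 | 0.0930 | 0.093 | 0.574 | 0.57 |
| 0.65 | 0.9035 | 0.904 | 0.046 | 0.05 |

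The figures reproduce, and they hold if every one of the 28 treated subjects counts.

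**2. One dataset, three ORRs.** Assumed case: 28 treated, 15 responders, 5 non-responders who stop in cycle 1 without progression, 2 of whom progress later while still followed.

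- Section 11.2: all 5 are out, because none was removed for progression. 15/(28 − 5) = 15/23 = 65.2%.
- Section 13.3.2 with the 5.6 meaning: the 2 later progressors return. 15/(23 + 2) = 15/25 = 60.0%.
- All treated: 15/28 = 53.6%.

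The spread is 65.2 − 53.6 = 11.6 points.

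**3. Direction of bias.** Suppose 15/25 = 60.0% is reported, 3 subjects are excluded, and k of the 3 had in fact responded. Bias = 60.0% − (15 + k)/28.

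| k | All-treated ORR | Bias (points) |
|---|---|---|
| 0 | 53.6% | +6.4 |
| 1 | 57.1% | +2.9 |
| 2 | 60.7% | −0.7 |
| 3 | 64.3% | −4.3 |

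The bias is upward unless the excluded subjects respond more often than those kept.

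**4. The decision rule at a true all-treated ORR of 40%.** The documents give no non-evaluable share d; 5% and 10% are assumed.

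- No replacement, cutoffs fixed at 6 and 15, all excluded subjects non-responders: no response is lost, and P(success) stays at 0.093.
- No replacement, fixed cutoffs, exclusion irrespective of response: p = 0.40(1 − d) = 0.38 or 0.36, and P(success) = 0.062 or 0.039.
- Evaluable subjects fill the 13 and 28, and all excluded subjects are non-responders: p = 0.40/(1 − d) = 0.421 or 0.444, and P(success) = 0.137 or 0.199.

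**5. Power if 65% is an evaluable-subject rate.** With 28 treated and excluded subjects contributing no response, p = 0.65(1 − d) = 0.6175 or 0.585, and power = 0.831 or 0.732.

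**The case against.** **The evaluable set is prespecified, so preferring all treated is the reviewer's choice.** This stands only in part. An evaluable-subject ORR can be prespecified, but this one is selected on post-treatment events, has two definitions, and does not match the enrolled counts in 13.2.

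**The off-study conflict is thinner than it looks.** This stands as to 5.5. A reader might take 5.5 as a rival definition. Its next sentence speaks of removal from protocol therapy, and it keeps these subjects under follow-up, so its opening is probably a slip for off-therapy. The loose use in Table 6-1 and 11.2 remains, and the 65.2% in the example needs only 11.2.

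**Early stoppers are scanned.** A reader might infer that no imaging is planned for them. That goes too far: the 10.3 CTs cover subjects without progression and are not limited to those who finished cycle 1. What remains is that the day 84 scan is not clearly assigned to them, and the first 10.3 CT is counted from an end-of-treatment scan.

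**Type I error is not shown to be inflated.** A reader might infer that it is 0.137 or 0.199. That needs evaluable subjects to fill the 13 and 28, every excluded subject to be a non-responder, and 40% to be an all-treated rate. The documents state none of these. Without replacement the rule can become conservative instead.

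**The size is hypothetical.** This stands. The any-time discontinuation rate for adverse events in Table 2-2 is not a cycle 1 rate and cannot supply d.

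**Conclusion.** The point holds and should be fixed. Sections 13.3.2 and 11.2 give a selected and non-unique denominator for the primary endpoint, while 13.2 counts enrolled subjects and no section scores cycle 1 stoppers without progression. Upward bias in the reported ORR is likely, because early stoppers would usually be expected to respond less often. It is not certain, because an early stopper with a CR or PR is dropped too.

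The size rests on assumed counts: up to 11.6 points between definitions in the example. No figure in 13.2 is wrong. Whether the go/no-go rule is unchanged, stricter or looser depends on replacement and on which subjects are excluded, and the plan settles neither.

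**What to change.** 1. **Sections 13.3.2 and 11.2:** use one definition. The primary ORR set is all subjects who receive any blinatumomab. A CR or PR counts as a response if documented by the end-of-treatment response assessment and before any new anticancer therapy. Everyone else, including subjects not restaged, is a non-responder. Keep the evaluable set as a labelled sensitivity analysis.
2. **Section 13.2:** state that 13 and 28 are treated subjects without replacement, and which population 40% and 65% describe. Footnote c of Table 2-6 limits the background response totals to patients who reached the highest target dose. The documents do not tie 40% or 65% to that table, so this is a question for the sponsor. If 65% is an evaluable-subject rate, restate power.
3. **Section 11.1:** state whether subjects who stop during cycle 1 have the day 84 assessment.
4. **Sections 5.5, 5.6, 11.2 and Table 6-1:** reconcile the off-study wording.

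The cost is wording, and a reported ORR that may be less favourable. If 40% and 65% are all-treated rates, sample size, type I error and power are unchanged. If 65% is an evaluable-subject rate, the lower power (0.831 or 0.732 at an assumed 5% or 10%) already applies on the literal 28-enrolled reading and is not a cost of this change. The sponsor would then accept it or revisit the sample size.

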APPENDIX A

PERFORMANCE STATUS CRITERIA

ECOG Performance Status Scale		Karnofsky Performance Scale	
Grade	Descriptions	Percent	Description
0	Normal activity. Fully active, able to carry on all pre-disease performance without restriction.	100	Normal, no complaints, no evidence of disease.
		90	Able to carry on normal activity; minor signs or symptoms of disease.
1	Symptoms, but ambulatory. Restricted in physically strenuous activity, but ambulatory and able to carry out work of a light or sedentary nature (e.g., light housework, office work).	80	Normal activity with effort; some signs or symptoms of disease.
		70	Cares for self, unable to carry on normal activity or to do active work.
2	In bed <50% of the time. Ambulatory and capable of all self-care, but unable to carry out any work activities. Up and about more than 50% of waking hours.	60	Requires occasional assistance, but is able to care for most of his/her needs.
		50	Requires considerable assistance and frequent medical care.
3	In bed >50% of the time. Capable of only limited self-care, confined to bed or chair more than 50% of waking hours.	40	Disabled, requires special care and assistance.
		30	Severely disabled, hospitalization indicated. Death not imminent.
4	100% bedridden. Completely disabled. Cannot carry on any self-care. Totally confined to bed or chair.	20	Very sick, hospitalization indicated. Death not imminent.
		10	Moribund, fatal processes progressing rapidly.
5	Dead.	0	Dead.

Appendix B – Amgen recommendations for notification of adverse events

Table 1- For Interventional studies with Amgen IMP*:

Safety Data	Timeframe for Submission to Amgen
Suspected Unexpected Serious Adverse Reaction (SUSARs)	Sent to Amgen at time of regulatory submission
Serious Adverse Events (SAEs)	Cumulative line listing every 6 months
Adverse Events not meeting serious criteria	Not required, unless contractually specified per study
Events of Interest	Not required, unless contractually specified per study
Pregnancy/Lactation	Within 10 days of Sponsor awareness
Event listing for reconciliation	As specified per contract, at study close-out at a minimum

*Specific requirements are to be outlined in the Research Agreement

Table 2 - For all studies – aggregate reports*:

Safety Data	Timeframe for submission to Amgen
Annual Safety Report (eg, EU Clinical Trial Directive [CTD] Annual Safety Report, and US IND Annual Report)	Annually
Other Aggregate Analyses (any report containing safety data generated during the course of a study)	At time of ISS sponsor submission to any body governing research conduct (eg, RA, IRB, etc)
Final (End of Study Report, including: 
 • Unblinding data for blinded studies • Reports of unauthorized use of a marketed product 	At time of ISS sponsor submission to any body governing research conduct (eg, RA, IRB, etc) but not later than 1 calendar year of study completion

*Specific requirements are to be outlined in the Research Agreement
